3.2.1 Intervention Arm Condition

All intervention arm activities may be conducted virtually.

Participants randomized to the intervention arm will receive:

PrEP Navigator: PrEP navigators will connect with participants following study onboarding. Navigators will serve participants across multiple clinics, primarily operating remotely, adapting workflow to participant and clinic needs. Primary navigator responsibilities include helping participants engage in PrEP care, assisting with completing necessary paperwork for insurance, referral to PrEP care, and application for drug assistance programs, as needed. All navigators will undergo study- and navigator-specific trainings (Sections 4.1 and 4.3). Navigation services will be available to all participants randomized to the intervention for up to 6 months – participants who are only followed for 3 months will by necessity only receive 3 months of navigation services.

Digital Health Intervention: HMP is an HIV status-neutral, theory-informed DHI to support sexual health and risk reduction among YSGM^{35–37}. HMP is guided by the Integrated Behavioral Model (IBM)³⁸ facilitating examination of the individual and structural determinants of health (e.g., stigma and discrimination, health literacy, poverty) and psychological distress (e.g., depression, anxiety, loneliness) which hinder adoption of HIV preventive behaviors. The app provides critical resources for persons regardless of readiness to initiate PrEP as well as ongoing support and resources for those who do initiate PrEP. The features of HMP are described in Table 1 and

example screenshots included in Figure 1. As part of PrEP monitoring features, participants can indicate how PrEP was prescribed (i.e. daily oral, event-driven oral, or injectable), as well as indicate dates PrEP was taken or, in the case of injectable, received.

Fig 1: HMP app screenshots

[figure not shown]

Table 1: The healthMpowerment (HMP 2.0) platform

| Administration Portal and mobile app (research staff-facing) | |
|---|--|
| Communication | Allows for participant management (two-way, secure, direct in-app messaging, and push notifications) |
| Study Management | Survey integration and incentive tracking |
| Calendar | View schedule of study visits and activities and send automated reminders |
| Analytics | Analytics dashboard to monitor app engagement and perform engagement analyses |
| Security | HIPAA compliant, encryption of data at rest and in transit |

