7.0 OUTCOME MEASURES AND DATA SOURCES

For interventions that address systems-level challenges or utilize patient navigation as an intervention component, PrEP uptake is an appropriate primary outcome as it is an indication of the success of the intervention to overcome the barriers to access to the health service/treatment^{42,43}. Given the current lack of PrEP availability in the proposed study settings, an intervention that can overcome the multi-level barriers to PrEP access and uptake is a critical first-step.

With PrEP uptake as the primary outcome and the primary objective to increase PrEP uptake, this study will follow a similar operational definition as another large-scale mHealth RCT intervention for PrEP uptake among MSM in the southern United States⁴⁴: self-report taking any PrEP (oral or injection) on a follow-up survey or in the app, AND verified by at least one of the following: (1) an uploaded photo or image demonstrating a PrEP prescription; OR (2) any indication of the presence of tenofovir diphosphate or cabotegravir in DBS; OR (3) staff-abstracted electronic medical record of PrEP prescription issued or physician notation of PrEP initiated.

Table 3 presents the study Outcome Measures and their data sources.

| Table 3: Study Outcome Measures and Data Sources | | | |
|--|---------------------------------------|---|---|
| Name | Time Frame | Brief Description | Data sources |
| Primary outcome | | | |
| PrEP uptake | 3-month follow-up | Verified self-reported PrEP use (first dose, oral or injectable) ¹ | CASI, in-app report, EHR abstraction, self-collected lab sample |
| Secondary outcomes | | | |
| PrEP uptake | 6-month follow-up ⁴ | Verified self-reported PrEP use (first dose, oral or injectable) ¹ | CASI, in-app report, EHR abstraction, self-collected lab sample |
| PrEP care engagement | 3- and 6-month ⁴ follow-up | Daily oral or event driven PrEP: after PrEP uptake, number and dates of any subsequent PrEP visits or new/refilled | CASI, EHR |

| | | | |
|--|--|--|--|
| | | PrEP prescriptions Injectable PrEP : after initial injection, number and dates of any subsequent PrEP visits/injections | |
| PrEP use | 3- and 6-month ⁴ follow-up | Number of consecutive months PrEP used, based on date of first and last dose ² | CASI, EHR |

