| PrEP adherence (self-report) | 3- and 6-month ⁴ follow-up | Daily oral PrEP : reported PrEP use (past 30 days) Event-driven PrEP : reported PrEP use corresponding to reported sexual activity (past 30 days) Injectable PrEP : based on date of injections | CASI |
| PrEP adherence (injection history & drug measurement) | 3- and 6-month ⁴ follow-up | Daily oral PrEP : PrEP concentrations detected at designated study follow-up visits, based on intraerythrocytic TFV-DP collected as DBS; Injectable PrEP : based on dates of injections | Self-collected lab sample, EHR |
| Incident STI/HIV | 3- and 6-month ⁴ follow-up | Clinical test result (yes / no / indeterminate / missing) for each STI and HIV that participant is tested for. | CASI; State, clinic, commercial lab results ³ |
| PrEP Stigma | 3- and 6-month ⁴ follow-up | Self-reported scored PrEP Stigma scale | CASI |
| Implementation measures (intervention arm and stakeholders) | | | |
| Fidelity-Engaged by PrEP navigator | First two weeks following enrollment | Proportion of Intervention Arm enrolled participants that are engaged by the PrEP navigator within two weeks of enrollment | Intervention CRF |
| Intervention satisfaction - Quantitative | 3- and 6-month ⁴ follow-up | Average score on participant-completed System Usability Scale (10 item universal measure of usability and acceptability). | CASI |
| Intervention satisfaction – Qualitative | 3- or 6-month ⁴ follow-up | Description of participant experiences and satisfaction, usefulness and attribution to PrEP use while on study and with each intervention component. | In-depth interviews with participants |
| Acceptability | Within 3-months before or after baseline and | Description of stakeholder experiences and acceptability of intervention, readiness for change, implementation | In-depth interviews and surveys with |

| | | | |
|--------------------------------|--|--|--|
| | within 3 months before or after study close-out | climate, and intervention values | stakeholders |
| Clinic measures | | | |
| STI service delivery | Baseline, 3- and 6-month ⁴ follow-up | Proportion of enrolled participants receiving STI screening (urogenital, rectal, pharyngeal) at baseline (pre-enrollment) and follow-up timepoints | State, clinic, commercial lab results ³ |

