¹ Persons who self-report taking any PrEP (oral or injection) during a follow-up survey OR in their app will meet this endpoint if this self-report is verified by at least one of the following: (1) an uploaded photo or image demonstrating a PrEP prescription; OR (2) any indication of the presence of tenofovir diphosphate or cabotegravir in DBS; OR (3) staff-abstracted electronic health record of PrEP prescription issued or physician notation of PrEP initiated.

² First dose and last dose determined based on self-report for oral PrEP and medical record (or self-report if record not available) for injectable PrEP. Respondents endorsing any PrEP dose will have uploaded current PrEP prescription as described in PrEP uptake outcome as above.

³ State, clinic and commercial labs: We will collect HIV/STI test results directly from laboratory portals or via secure upload of results from participants or participating clinics' medical records.

⁴ Participants who reach 6-months of study follow-up prior to study end will contribute to 6-month outcome measures.

⁵ Participants who reach 12-months of follow-up prior to study end (see 17.0 Timeline) will complete a brief CASI survey inquiring about PrEP use, including PrEP uptake and any interruptions or discontinuations of PrEP. They will also maintain ability to self-report PrEP start within the app through month 12. Self-reported STI and HIV results will also be captured at this time point, as well as preferences for provision of extended PrEP navigation resources.

⁶ Persons who self-report taking any PrEP (oral or injection) during a follow-up survey OR in their app will meet this endpoint if this self-report is verified by at least one of the following: (1) an uploaded photo or image demonstrating a PrEP prescription; OR (2) staff-abstracted electronic health record of PrEP prescription issued or physician notation of PrEP initiated. DBS samples will not be collected at month 12.

⁷ All participants (intervention and control) will be asked questions on CASI about PrEP use, medication adherence and sexual behavior; CASI data will be used to calculate an estimate of effective protection for **all** participants. In-app daily medication adherence self-report and daily sexual behavior self-report are only available for intervention arm participants; in-app data will be used to calculate an app-based estimate of effective protection for any **intervention arm** participants who used the app to record these behaviors.

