| Y3 (end of trial) | (6) Among intervention arm PrEP initiators, ≥50% sustain use ≥3 months | Among participants in the intervention arm who have initiated PrEP and for whom 3-months of study follow-up time has elapsed since PrEP initiation, at least 50% will sustain PrEP use for ≥3 months as indicated by engagement in PrEP care (on-time visits/refills/injections) and self-reported PrEP use. Any other scenarios would be at the discretion of NIH. We will also report the number of participants who initiate PrEP after their 3-month study visit and thus have less than 3-months of available PrEP sustainment data at their 6-month follow-up visit. |
| R33 | | |
| | Established relationship with HD stakeholders and letters of support | |
| | Refined strategy approved by key stakeholders for implementation | |

| | | |
|--|--|--|
| | Interactive costing interface platform finalized | |
| | Refined strategy $\geq 75\%$ effective (PrEP uptake) vs R61 intervention | |

^a Year 1 refers to the RCT pre-implementation phase aligning with the grant timeline (Budget Period 1: June 13, 2022 – May 31, 2023).

^b Because participants for whom intended follow-up is limited to 3-month outcomes are scheduled to have only 1 DBS, criteria for these participants is as follows: $\geq 50\%$ have completed the 3-month survey, and $\geq 50\%$ have returned 1 DBS. Any other scenarios would be at the discretion of NIH.

^c The original grant proposal specified this milestone as pertaining to PrEP uptake at a clinic level compared to "pre-intervention baseline". However, this is not applicable because revisions to the study now specify randomization will be at the individual (rather than clinic) level with comparison of intervention versus a concurrent control arm. This change describes the effect of the intervention above background uptake in the control arm during the same time (e.g., to control for secular trend). Power analysis suggests that this milestone will reach statistical significance at a 7.5% difference, as clarified in the definition.

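### The PrEP use outcome is labelled as consecutive months but is built from first and last dose dates, so it measures elapsed time and not uninterrupted use

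*Combined protocol and SAP*

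**What the plan says.** Table 3 lists PrEP use as a secondary outcome at 3 and 6 months and defines it as "Number of consecutive months PrEP used, based on date of first and last dose". The exploratory 12-month row repeats the definition. The listed sources are CASI and EHR. Footnote 2 says where the two dates come from: "First dose and last dose determined based on self-report for oral PrEP and medical record (or self-report if record not available) for injectable PrEP". It does not mention doses between those dates. Section 9.2.2 sends all secondary outcomes back to Section 9.2, which compares continuous endpoints by the Wilcoxon rank-sum test and says nothing about gaps or restarts.

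The plan expects three regimens. Section 3.2.1 describes PrEP prescribed as "daily oral, event-driven oral, or injectable". The self-reported adherence outcome treats them separately and judges event-driven users on "reported PrEP use corresponding to reported sexual activity (past 30 days"). PrEP use has one rule for all three.

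Interruptions are named in footnote 5, which describes the 12-month survey as "including PrEP uptake and any interruptions or discontinuations of PrEP". That item is not linked to the PrEP use calculation. Sustained use under milestone 6 (Section 11.0, Table 6) is assessed in the intervention arm only, "as indicated by engagement in PrEP care (on-time visits/refills/injections) and self-reported PrEP use".

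**The concern.** The label and the computation disagree within one table cell. Consecutive months is a statement about continuity, whereas a first date and a last date carry only elapsed time. Someone who stops early and takes a single dose months later gets the same score as someone who took PrEP throughout.

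The study title names persistence as well as uptake, and this is the only secondary outcome expressed as a duration of use. A reader of the results would take a between-arm comparison of consecutive months as evidence on persistence. Under the stated rule it would partly reflect how far apart the first and last doses happened to fall.

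**Working it through.** No stated sample size, power or error rate depends on this definition, so there is no figure in the plan to reproduce. The check compares what the stated rule returns with what the label promises.

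**Step 1: the inequality.** For dose dates running from D(first) to D(last), the span is D(last) − D(first), which equals the sum of all runs of use plus the sum of all gaps between them. The longest uninterrupted run is one of those runs. The span is therefore never shorter than the longest run between doses, and the two are equal only when there is no gap.

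**Step 2: dose calendars.** Span in months = (last day − first day + 1) / 30.4375. The dosing patterns are assumptions, and so is treating a gap of more than 30 days as a break. Neither is a proposal for the trial.

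| Assumed pattern | Span (months) | 30-day blocks with any dose | Longest run (months) |
|---|---|---|---|
| Daily, 180 days, no gap | 180/30.4375 = 5.9 | 6 | 5.9 |
| 30 days on, 120 off, 30 on | 180/30.4375 = 5.9 | 2 | 30/30.4375 = 1.0 |
| 60 days on, 60 off, 60 on | 5.9 | 4 | 60/30.4375 = 2.0 |
| Event-driven, two 3-day episodes (days 0–2 and 177–179) | 5.9 | 2 | not meaningful |
| One injection | 1/30.4375 ≈ 0 | 1 | ≈ 0 |

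The first three rows score identically under the stated rule. A more extreme case, one dose on day 5 and one on day 175, gives 171/30.4375 = 5.6 months for two doses.

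The last row shows the opposite error. One injection gives a span of about zero. With several injections, any cover after the last one is left out.

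**Step 3: how the excess depends on intermittency.** Assume six monthly blocks, use in block 1, and independent probability q of use in each later block. Expected months with any use = 1 + 5q. Expected span = 1 + Σ(j=1..5) [1 − (1 − q)^j]. At q = 0.4 these are 1 + 2.0 = 3.0 and 1 + (0.400 + 0.640 + 0.784 + 0.870 + 0.922) = 4.62. A simulation of 40,000 users per value of q gave these means:

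| q | Span | Months with any use | Longest run |
|---|---|---|---|
| 0.20 | 3.31 | 2.00 | 1.34 |
| 0.40 | 4.61 | 3.01 | 1.97 |
| 0.60 | 5.34 | 4.00 | 2.87 |
| 0.80 | 5.75 | 5.00 | 4.16 |
| 0.95 | 5.95 | 5.75 | 5.48 |

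The excess of span over longest run is large for intermittent users and small when use is nearly continuous.

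**Step 4: how many participants could be affected.** On the planning assumptions in Section 9.1 (336 randomized 1:1, so 168 per arm; 2.5% control uptake; a 7.5-point difference), 3-month initiators would number 168 × 0.025 = 4.2 in the control arm and 168 × 0.10 = 16.8 in the intervention arm, before missing data. Only initiators with a gap, or on injectable PrEP, are mis-scored. The documents give no interruption rate and no split by regimen, so the calculation stops there.

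**The case against.** The strongest reply is that the Table 3 column is headed as a brief description, and that consecutive can be read as a condition, so that the two dates are the ends of one unbroken run. That reading is possible. Nothing in the documents adopts it, however, and no fuller derivation appears in the footnotes or in Section 9. An analyst following footnote 2 would take the two dates and subtract.

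A second reply is that other measures are sensitive to gaps. Care engagement records dates of visits, refills and injections. Self-reported oral adherence covers the past 30 days. Effective HIV protection is a proportion of days, estimated from CASI for both arms. Milestone 6 uses on-time care. These exist, but none corrects this outcome: care engagement is a separate endpoint, a 30-day look-back misses earlier gaps, effective protection is exploratory, and milestone 6 makes no between-arm comparison.

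Four stronger readings are tempting, and the documents do not support them:

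- **The rule always errs towards longer use.** It does not; the injectable case runs the other way.
- **The error favours the intervention arm because navigators prompt restarts.** Navigators are trained to support maintenance and serve only that arm, so the idea is reasonable, but no figure or statement on restart rates supports it.
- **The 3- and 6-month surveys omit interruptions.** Footnote 5 describes the 12-month survey only, the questionnaires are not in the documents, and footnote 7 says all participants are asked on CASI about PrEP use and adherence.
- **A gap in event-driven dosing is a failure to persist.** A gap with no sexual activity need not be one, and the plan does not say what a month of use means for these users.

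**Conclusion.** The point holds as a defect in one secondary outcome at 3 and 6 months and its exploratory 12-month counterpart. As written, the rule returns elapsed time under a label that promises continuity. It overstates uninterrupted use for oral users who interrupt, and it can understate use for injectable users. The illustrated excess ranges from nothing (no gap) to 4.9 months (5.9 − 1.0, for 30 on, 120 off, 30 on), but those patterns are assumed. The size of the error in this trial and any imbalance between arms are unknown.

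A reader might infer that the effectiveness conclusion or the Go/No-Go decision is affected. It is not: neither the primary outcome nor milestone 6 uses this measure. This is a worthwhile correction of low severity.

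**What to change.** Before analysis:

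1. For daily oral and injectable PrEP, derive the uninterrupted run from the refill, visit, injection and self-reported dates already collected through CASI and EHR. Pre-state an analytic gap rule for each regimen, how time after the last recorded dose is counted, and whether the first or the longest run is reported. The investigators should set the gap lengths. Use sources common to both arms, since daily in-app tracking exists only in the intervention arm.
2. Report total covered months alongside the run.
3. Report event-driven users separately and without a fixed-gap rule, which would score appropriate use as stopping. Use relative to reported sexual activity, as in the plan's own adherence outcome, is one option. Its 30-day look-back describes recent use, not duration.
4. Confirm that the 3- and 6-month CASI capture interruption dates. If they do not, add the 12-month item.
5. If none of this is done, rename the outcome time from first to last dose and do not interpret it as consecutive use.

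The cost is an edit to the definition, a small amount of derivation work and possibly one survey item. Sample size and the primary analysis are unchanged. If follow-up is already under way, a new survey item helps only participants not yet assessed.

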3.0 STUDY DESIGN

The Phase 1 study is a randomized trial of a multilevel intervention to increase access to, uptake of, and maintenance on PrEP for HIV prevention. Participants will be randomized to an intervention or control condition (Section 3.2). The primary outcome is PrEP uptake within 3 months of an index STI clinic visit, assessed using drug metabolite presence, chart review, and self-report. All study participants will have access to study management functions as a DHI platform (HMP). Participants randomized to the intervention condition will receive the multilevel intervention (Section 3.2.1) while those randomized to the control condition will receive the informational resources component of the DHI (Section 3.2.2). Participants will complete study measures and activities at baseline and 3- and 6-month follow-up timepoints, with a subset of participants also completing 12-month follow-up (refer to Table 2.2) Participants enrolled in approximately the last 3 months of enrollment, will be followed for 3 months (refer to Table 2.3). We will assess implementation and process outcomes and organization-level determinants of success to inform future refinement.

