9.0 STATISTICAL/ANALYTIC CONSIDERATIONS

9.1 Sample Size and Power Estimate

We expect > 7,400 patients will present for care in the 21-month enrollment period, with 20-35% study eligible. Aim 1 analysis includes eligible, consenting patients who successfully download the HMP app. The study will enroll for 21 months with a target sample size of 336. We expect approximately half of participants will be randomly assigned to the intervention arm and the remaining half to the control arm (see Randomization, Section 3.2).

We calculated statistical power for the effect of intervention upon PrEP uptake by 3-month follow-up using SAS 9.4 (Cary, NC) with a 5% type I error rate and a two-sided Chi-square test. Assuming 2.5% of eligible patients start PrEP within 3 months in the control arm, we calculated statistical power to detect a range of small to large effect sizes from 5% to 15% percentage point increases in PrEP uptake under a range of possible sample sizes and assuming 10% missing data (Table 4). At a total sample size of 336, given our design and assumptions, we will have >88% statistical power to detect medium (10%) and large (15%) effect sizes, and 80% statistical power to detect a moderate (7.5%) effect size.

Effect size rationale: As there is currently limited-to-no infrastructure or existing programming providing PrEP in rural North Carolina STI clinics, no prior studies that we are aware of have measured PrEP uptake in these settings. Overall, U.S. PrEP coverage of those assigned male sex at birth with PrEP indications was reported by CDC as 18.4% in January – March 2021, but only 5.6% among Black/African American⁴⁶, who will constitute a large portion of our sample. Among the CDC-designated End-the-Epidemic jurisdictions, recent PrEP coverage estimates of those with PrEP indications range from a low of 4.5% in San Bernardino to a high of 42.3% in San Francisco; North Carolina's state level PrEP coverage estimate is 13.3%, which belies the wide variability from

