9.2 Outcome Analysis

Eligible participants will enter the study within 45 days of screening as eligible and will be followed longitudinally for PrEP uptake for up to 12 months. Analyses will be conducted for all primary and secondary outcomes defined in Table 3 (Section 7.0) using the following general procedures for analysis.

Basic descriptive statistics will be calculated. Frequency tables will be presented for the categorical variables and means, standard deviations, and percentiles (25th, 50th, 75th) will be given for the continuous variables. For each binary outcome, we will estimate the proportion of patients achieving the event (e.g., PrEP uptake) in each arm and a probability difference (PD) and a corresponding 95% confidence interval (CI) to compare the intervention vs. control arms at each timepoint (3-month, 6-month, and 12-month follow-up). For continuous endpoints, we will use a non-parametric Wilcoxon Rank-Sum Test to compare the intervention and control arms. For count

data variables (e.g., number of unprotected sex acts), we will use small analysis methods for count data (e.g. exact Poisson regression).

To address missing data, we will review the frequency of missing and non-missing values for all variables at baseline, 3-month, 6-month, and 12-month follow-up. We will conduct missing value analyses to determine whether persons with missing values are systematically different from those without missing values and if the probability of having missing values differs by arm. If this assessment of the frequency and imbalance of missing data suggests that bias may be introduced, we will employ inverse probability of observation weights or multiple imputation to address the missing data.

If there is chance imbalance in the measured baseline covariates, we will conduct sensitivity analyses applying stabilized inverse probability treatment weights (IPTW).

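### Later PrEP uptake is a cumulative first-dose outcome, but the plan compares it as simple proportions among those who reach 6 or 12 months, under a different verification rule at month 12

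*Combined protocol and SAP*

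**What the plan says.** - **The event.** Table 3 defines uptake at 3, 6 and 12 months as verified, self-reported use, specified as the first dose. The synopsis words the 6-month secondary outcome as uptake in the six months after the index visit.
- **Who counts later.** Footnote 4: "Participants who reach 6-months of study follow-up prior to study end will contribute to 6-month outcome measures". Footnote 5 gives the 12-month survey only to those who reach month 12 before study end. Section 3.0 adds: "Participants enrolled in approximately the last 3 months of enrollment, will be followed for 3 months". The synopsis describes the same group as roughly the final quarter of enrolment.
- **Analysis.** For binary outcomes, section 9.2 estimates a proportion per arm and a probability difference with 95% CI, "to compare the intervention vs. control arms at each timepoint (3-month, 6-month, and 12-month follow-up"). It names no time-to-event or cumulative-incidence method. Weighting or multiple imputation follows only if missingness suggests bias.
- **Verification.** At 3 and 6 months (footnote 1), a self-report in a survey or the app can be verified by prescription image, dried blood spot (DBS) or health record. At 12 months (footnote 6) only the image and the record remain, because "DBS samples will not be collected at month 12". Section 9.2.4 says instead that every 12-month measure is self-reported by survey.
- **Dates.** The PrEP use outcome is "based on date of first and last dose", so first-dose dates are collected. For oral PrEP they are self-reported (footnote 2).

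**The concern.** A first dose, once verified, cannot be undone, so cumulative uptake in a fixed group can only rise. The planned summaries do not guarantee this, for three reasons.

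1. The denominator changes. Late enrolees contribute to 3-month uptake and then leave the 6-month set, although their first three months were observed.
2. The verification rule changes at month 12.
3. No sentence says whether a start verified at one time counts at later times. For example, the plan does not say how to classify a participant verified at month 3 who misses the 6-month survey. That survey has a 30-day window (Table 2.2), and milestone 4 accepts 50% completion, so the case need not be rare. Two analysts following the plan could report different 6-month results.

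At stake are one secondary outcome (6 months), one exploratory outcome (12 months), and any reading of the three figures as a trajectory.

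**Working it through.** **The plan's own figure.** The documents give no sample size, rate or power for 6- or 12-month uptake. The only power statement at N = 336 is for month 3: "80% statistical power to detect a moderate (7.5%) effect size", "with a 5% type I error rate and a two-sided Chi-square test", with control uptake of 2.5% and 10% missing data. That leaves 168 × 0.9 = 151.2 per arm. For 2.5% vs 10%, the pooled normal approximation gives 77.1%, and exact power of the Pearson chi-square at 151 per arm gives 79.7%. The stated 80% is reproduced by the exact calculation, so I use 151 per arm below.

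**Participants left out at 6 months** (even accrual assumed): 3/21 = 14%, or 48 of 336, on the section 3.0 wording; 25%, or 84 of 336, if the synopsis means a quarter of participants. That leaves 288 or 252. If the 6-month contrast were also 2.5% vs 10% with 10% missing, the pooled formula would give 70.6% or 64.7% power, against 77.1% at 336.

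**Precision: planned proportion vs Kaplan-Meier on everyone.** Let F be cumulative uptake, n = 151 per arm and s the share reaching the time point.

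- Planned: variance per arm = F(1−F)/(n·s).
- Kaplan-Meier at 6 months (Greenwood), where q₁ and q₂ are the conditional probabilities of starting in months 0-3 and 3-6: (1−F₆)²·[q₁/((1−q₁)n) + q₂/((1−q₂)·n·s·(1−F₃))]. A third term of the same form extends it to 12 months.

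Uptake after month 3 is not in the documents, so two assumed patterns at 3/6/12 months are used: A, 10/15/19% vs 2.5/4/6%; B, 10/12/14% vs 2.5/3/4%. Assumed shares reaching 6 and 12 months are 18/21 and 12/21 (follow-up ending 3 months after the last enrolment), or 75% and 50%.

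Worked case, pattern A at 6 months, s = 18/21:

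- Planned: 0.15×0.85/(151×0.857) + 0.04×0.96/(151×0.857) = 0.000985 + 0.000297 = 0.001282; half-width 1.96×√0.001282 = 7.0 points.
- Kaplan-Meier, intervention: q₂ = 0.05/0.90; 0.85²×[0.1111/151 + 0.0588/(151×0.857×0.90)] = 0.000896.
- Kaplan-Meier, control: q₂ = 0.015/0.975; 0.96²×[0.02564/151 + 0.01563/(151×0.857×0.975)] = 0.000271.
- Sum 0.001167; half-width 6.7 points; variance ratio 0.91.

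| Pattern, shares | 6 months: ratio; half-width | 12 months: ratio; half-width |
|---|---|---|
| A, 86% / 57% | 0.91; 7.0 → 6.7 | 0.71; 9.7 → 8.2 |
| A, 75% / 50% | 0.84; 7.5 → 6.9 | 0.68; 10.3 → 8.5 |
| B, 86% / 57% | 0.88; 6.3 → 5.9 | 0.67; 8.4 → 6.9 |
| B, 75% / 50% | 0.80; 6.8 → 6.0 | 0.62; 9.0 → 7.1 |

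Variance falls by 9-20% at 6 months and 29-38% at 12 months.

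**Can reported uptake fall?** One arm of 168 was simulated with 10% uptake by month 3, every starter carried forward, and 14% to 25% leaving the denominator at month 6. The chance that the 6-month proportion is below the 3-month one is:

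- 3% to 6% if true 6-month uptake is 13%;
- 20% to 24% if it is 11%;
- about 45% if nobody new starts.

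If late enrolees start 5 points more often, the first two become 9% to 19% and 40% to 53%.

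**The 12-month rule.** With 10% uptake by month 3, 2 points of new starts and a share d of month-3 starts verified by DBS alone, the literal rule gives 10(1−d) + 2 points. This is below 10 once d exceeds 20%. The documents give no value for d.

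**The case against.** **Re-measurement is not stated.** A reader might infer that the plan measures uptake afresh at each visit and treats a month-3 starter who misses the 6-month survey as missing. The documents do not say so. The cumulative wording, the first-dose definition and the acceptance of any follow-up survey or app report all fit carrying a start forward. Footnote 4 turns on elapsed follow-up, not on completing the survey. Footnote 6 explains that no DBS is taken at month 12 and does not expressly revoke an earlier start. This stands: the fault is silence plus a literal 12-month rule.

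**The restricted proportion is valid.** Eligibility for later follow-up depends on enrolment date, and randomisation is blocked within county, so the arms should stay close to balanced. This stands: the loss is information and comparability.

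**The gain is small.** At 6 months the half-width shrinks by 0.3 to 0.8 points. The larger gain falls on an exploratory outcome. This stands, and it limits the weight of the point.

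**Pooling mixes two lengths of navigation.** This does not stand. Participants followed for 3 months would contribute only months 0-3, when navigation is available to the whole intervention arm.

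**Kaplan-Meier brings its own problems.** Curves stratified by enrolment period could leave a late stratum with nobody at risk after month 3, which removes the gain. With at least 15 counties, 168 per arm is about 11 per county, and 2.5% of 168 is about 4 control starts by month 3. Censoring everyone at scheduled end would also treat non-responders as event-free. These objections stand, and the fix avoids both.

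**Conclusion.** The concern holds in a limited form. Later uptake is defined cumulatively but analysed as separate proportions in shrinking sets. The plan has no carry-forward rule, its 12-month verification rule would literally drop DBS-only starts, and footnote 6 disagrees with section 9.2.4. The avoidable variance is about 9-20% at 6 months and 29-38% at 12 months. These figures rest on even accrual, 151 evaluable per arm, the assumed uptake patterns and an unstratified estimator.

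Three stronger readings are not supported. Nothing shows clear bias between arms. The 3-month primary outcome is untouched. A reader might also infer that 12-month results reflect only early sites, but footnote 5 selects participants by when they enrolled, not by site, and about half could reach month 12 under the assumptions above.

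**What to change.** 1. State that a start verified by any route, DBS included, counts at every later time point, whether or not the later survey is completed. Reconcile footnote 6 with section 9.2.4 on whether 12-month uptake needs verification.
2. Estimate cumulative uptake at 6 and 12 months, and the arm difference with 95% CI, by Kaplan-Meier on all randomised participants. Censor at the end of scheduled follow-up or when uptake status was last ascertained, whichever is earlier. Do not stratify the curves by county or enrolment period.
3. Report the planned proportion among those who reach each time as a sensitivity analysis.
4. Compare 3-month uptake by enrolment period.

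The cost is SAP wording and a few lines of code, with no new data. Two limits should be stated. The estimator assumes that enrolment date is unrelated to later uptake, which item 4 checks only in part. Oral first-dose dates are self-reported, so some will be imprecise or absent. The 3-month primary analysis stays as planned.
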